**STUDY SUMMARY:**

Investigational Agent(s) (Drugs or Devices)	NA
IND / IDE / HDE #	NA
Indicate Special Population(s)	 Children  Children who are wards of the state  Adults Unable to Consent  Cognitively Impaired Adults  Neonates of Uncertain Viability  Pregnant Women  Prisoners (or other detained/paroled individuals)  Students/Employees
Sample Size	16
Funding Source	NIDA
Indicate the type of consent to be obtained	 Written  Verbal/Waiver of Documentation of Informed Consent  Waiver of HIPAA Authorization  Waiver/Alteration of Consent Process
Site	 Lead Site ( For A Multiple Site Research Study)  Data Coordinating Center (DCC)
Research Related Radiation Exposure	 Yes  No
DSMB / DMC / IDMC	 Yes  No

STU#:

## LIST OF ABBREVIATIONS

ANCOVA	Analysis of Covariance
ANOVA	Analysis of Variance
BDI	Back Depression Inventory
BDI-II	Back Depression Inventory, Second Version
BP	Brain Properties
CBP	Chronic Back Pain
CESM	Cognitive Emotional Sensory Motor
CNS	Central Nervous System
CTA	Chicago Transit Authority
dMRI	diffusion Magnetic Resonance Imaging
EDW	Enterprise Data Warehouse
FC	Functional Connectivity
GMV	Gray matter volume
HIPAA	Health Insurance Portability and Accountability Act
Hipp	Hippocampus
Hz	Hertz
MQSIII	Medication Quantification Scale, third version
MRI	Magnetic Resonance Imaging
NAc	Nucleus Accumbens
NIH	National Institutes of Health
NMG	Northwestern Medical Group
NMH	Northwestern Memorial Hospital
NRS	Numeric Rating Scale
NU	Northwestern University
PAG	Periaqueductal Gray
PDQ	Pain Detect Questionnaire
PHH	Personal Health History
PHI	Protected Health Information
PIDs	Participation identification numbers
REDCap	Research Electronic Data Capture
rsfMRI	Resting State Functional Magnetic Resonance Imaging
rTMS	Repetitive Transcranial Magnetic Stimulation
SC	Central Sensitization
SEM	Structural Equation Modeling
[name]	[name]
TMS	Transcranial Magnetic Stimulation
VBM	Voxel-based morphometry

STU#:

**OBJECTIVES:**

*(Describe the purpose, specific aims, or objectives. State the hypotheses to be tested.)*

Chronic back pain (CBP) can last from months to a lifetime, severely impacting patients' quality of life. Based on our human brain imaging studies and preclinical findings, the hippocampus and its network are associated with pain and pain experience in patients with chronic pain. In this study we aim to test whether a non-invasive enhancement of dorsal hippocampus activity leads to networks alteration that can modulate pain in CBP patients.

**Aim 1:** To investigate whether a novel target, dorsal hippocampus, indirectly stimulated using high frequency rTMS, will lead to an increase in hippocampal network connectivity that can modulate pain, as compared a sham control rTMS, in CBP patients.

We hypothesize that changes in pain from baseline to post-stimulation will be superior for hippocampal-target than for control stimulation (sham). Pain is primarily assessed by daily ratings on our phone app; additional questionnaires will be used as secondary exploratory outcomes.

**BACKGROUND:**

Pain is the primary reason why people seek healthcare. Everyday millions of Americans are either partially or totally disabled due to pain. If untreated, this pain can lead to depression, insomnia, depressed immune function, changes in eating patterns, impaired cognitive function, and other long-term deleterious effects commonly associated with chronic pain. Chronic back pain constitutes the major form of chronic pain, with a prevalence as high as 70-85% in adults at some time in their lives. In the US, low back pain is the most common cause of activity limitation in adults younger than 45 years of age and the second most frequent reason for physician visits. Estimates from other countries support the fact that low back pain is one of the major - if not the major - cause of work absence, and therefore results in a significant burden to both the economy and health care system.

Current treatments for CBP involve the use of nonsteroidal anti-inflammatory drugs, antidepressants, and/or anticonvulsants or opioids. These carry relatively high risks yet show limited success rates, leading investigators to explore non-invasive interventions that in combination with conventional treatments, may produce greater pain relief in CBP.

Chronic back pain is associated with many negative affective mood disorders, and cumulative evidence suggests an association of hippocampal networks and chronic pain. Previous research performed by our group has shown the hippocampal circuitry being involved in the transition from acute to chronic pain, and hippocampal mechanisms such as diminished hippocampal neurogenesis. Moreover, abnormal glutamatergic activity was previously described in animal chronic pain models and bilateral hippocampal deactivation during innocuous stimulation in neuropathic patients. Therefore, our group conducted an animal study using chemogenetics or direct GLU injection to increase dorsal hippocampal glutamatergic activity and modulate pain. This demonstrated the analgesic effects of hippocampal stimulation; since increases in excitability of dorsal hippocampal neurons altered resting state connectivity (rsfMRI) within hippocampal networks that are specifically related to neuropathic behavior (tactile allodynia), thus indicating the potential for hippocampal stimulation in the management of chronic pain. Considering the previously established role of the hippocampus in pain perception, and its

STU#:

morphological changes in chronic pain, there is now impetus for investigating hippocampal excitation in chronic pain relief. With this in mind, we reason that in humans, by modulating local hippocampal circuits, we can directly target chronic pain.

In this pilot study, we aim to indirectly stimulate the dorsal hippocampus to increase hippocampal connectivity and modulate pain. We will use rTMS to stimulate an area of the parietal cortex with high functional connectivity to the hippocampus, using seed-based connectivity analysis of rsfMRI data, in order to modulate hippocampal-mediated networks. It is notable that targeting hippocampal excitability using rTMS is an approach that we have pioneered. The hippocampus is not directly accessible to rTMS. We use cortical “access windows”, which are stimulation-accessible areas of the cortex that have high connectivity with the hippocampus and therefore stimulation applied to these areas can indirectly influence the hippocampus. In several experiments. We have shown that this method increases excitability and rsfMRI connectivity of dorsal hippocampus, leading to long-lasting improvements in hippocampal-dependent function. We hypothesize that dorsal hippocampal stimulation will lead to analgesic effects in CBP.

In line with the promising preclinical results we report, in this study we will collect preliminary data to systematically test whether the modulation of hippocampal network changes the experience of pain in CBP patients.

## **STUDY ENDPOINTS**

This is a mechanistic study; therefore, the main study aim is to show that the hippocampal stimulation leads to functional connectivity changes across series of hippocampal networks and how these connectivity changes are correlated with pain decrease.

The secondary outcome will be changes in pain ratings. The effects of the brain stimulation will be measured by daily pain ratings (painApp) and questionnaires, using our in-house pain app. As we collect these outcomes repeatedly, we will have changes in pain immediately after the stimulation session and also over the next 2-weeks. We will test immediate and 2-weeks changes in painApp ratings relative to baseline. Questionnaire analyses, and other time course analyses of painApp data will be treated as exploratory in nature.

## **STUDY INTERVENTION(S) / INVESTIGATIONAL AGENT(S):**

### **Brain Stimulation**

For the brain stimulation we will use Repetitive Transcranial Magnetic stimulation (rTMS). The sessions will be performed at either the CTI or the LHN. Repetitive TMS parameters are determined based on the allowable dosage of rTMS delivery, calculated based on published standards for experimental rTMS protocols, and in accordance with standard operating procedures for rTMS. Previous studies have shown that four or more rTMS sessions are needed to induce changes in the hippocampal network connectivity.

The brain stimulation can be delivery using different devices; in this project we will use a MagPro X100 stimulator connected to a MagPro Cool-B65 liquid-cooled butterfly coil (MagVenture A/S, Farum, Denmark). Resting motor threshold (M1-rTMS) will be determined during the visit 1 or visit 2 and used along the 10 visits. Single TMS pulses are delivered to the thumb-control area of the brain's primary motor cortex and the pulse intensity required to reliably evoke movement of the thumb is determined. This value is used as each individual subject's “motor threshold”, and stimulation is delivered at a proportion of the motor threshold.

STU#:

The rTMS pulse sequences and intensities used are all within the published safety guidelines.

As different stimulation conditions (hippocampal, M1 or sham) will be delivered in each of the three rounds of stimulation, participants will be told that stimulations can feel and sound different. All participants will receive all the 3 modalities of stimulation following specific order (see details below).

- **Stimulation Modality 1- Hippocampus-stimulation:**

Repetitive TMS will be applied at 100% resting motor threshold intensity to a region of interest located in the parietal cortex, that will be determined based on its connectivity with the hippocampus. This stimulation consists of a series of 1,600 pulses administered as 2-second periods of 20 Hz pulse trains separated by 28-s inter-train intervals (~20 minutes for the entire daily stimulation session). The induced current field will be oriented perpendicular/anterior to the long axis of the gyrus encompassing the stimulation location.

- **Stimulation Modality 2-Sham-stimulation:**

Parameters will be identical to the hippocampus-stimulation, except that the coil will be flipped over to the sham side and a stimulating electrode will be attached to the skin near the parietal rTMS target location. This electrode will be used to deliver a small current mimicking real stimulation sensation, therefore participants cannot reliably discriminate physical sensations for real versus sham rTMS.

A trained co-investigator on the study will administer the rTMS. Prior to performing any study procedures, the study staff member will be trained in the techniques of rTMS as well as all aspects of the evaluations. This study staff member will then be evaluated by the PI of the study. The PI will then give confirmation that the co-investigator is qualified to administer the stimulation and the evaluations. Subjects are allowed to miss up to 1 stimulation visit in each treatment round, we will drop out subjects that miss more than 1 stim visit per round.

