#### **Stimulation modality sequences:**

The order of the stimulation modalities will be different across subjects. Subjects will be randomly assigned to one of two possible groups/stimulation sequences (fig 1). Before enrollment starts, we will produce 18 envelopes containing the stimulation sequence (see below possible combinations; we expect to use only 16). The stimulation sequence will be kept in sealed envelopes; therefore, subjects will get their assignment according to the order of entrance in the study. The study coordinator will retain the original sequence list which will be kept in a locked place. The study staff who provides the stimulation TMS session will be the only un-ed personnel.

STU#:

[figure not shown]

Figure 1: Study design and stimulation sequence. The subjects will be allocated to 1 envelop according to the entrance in the study. All participants will receive all the 2modalities of stimulation. Each round is composed by 5 daily session of stimulation, participants will not know which round is active and which is sham. Participants randomized to group 1 will have a second MRI at visit 6; and participants randomized to group 2 at visit 11.

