At visit 2, the stimulation protocol will start, and participants will receive a total of 10 sessions: 5 consecutive daily sessions of each stimulation round following the prior stimulation sequence order, interleaved by 2 weeks of wash out period. All subjects will undergo sessions of sham, and hippocampal-stimulation, in a crossover manner. As different stimulation conditions (hippocampal, M1 or sham) will be delivered in each of the two rounds of stimulation, participants will be told that stimulations can feel and sound different.

Before stimulation, the subjects will complete the following assessments:

- NRS for back pain

After each session, subjects will complete the following assessments:

- Side Effects Questionnaire for rTMS
- NRS for back pain
- At visits 6 and 11 participants will also complete the following questionnaires:
  - PainDetect;
  - Short-form Montreal Pain Questionnaires (sfMPQ);
  - BDI

Global impression of changeAfter the end of Round 1 or Round 2:

- MRI

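### The sham set-up adds a skin electrode that active sessions are not said to have, so in this crossover the participant blind is not assured and is never checked.

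*Combined protocol and SAP*

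**What the plan says.** **Active stimulation** (Brain Stimulation, Modality 1): "Repetitive TMS will be applied at 100% resting motor threshold intensity to a region of interest located in the parietal cortex". Pulse number, train pattern and current orientation follow. No electrode is mentioned.

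**Sham stimulation** (Brain Stimulation, Modality 2): "Parameters will be identical to the hippocampus-stimulation, except that the coil will be flipped over to the sham side", and, within the same exception, "a stimulating electrode will be attached to the skin near the parietal rTMS target location". The electrode carries a small current intended to imitate real stimulation. From this the protocol concludes that "participants cannot reliably discriminate physical sensations for real versus sham rTMS".

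**Design** (Visit 2–11 description): "All subjects will undergo sessions of sham, and hippocampal-stimulation, in a crossover manner". There are two rounds of five daily sessions, separated by a two-week washout.

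**The blind** (Figure 1 legend): "participants will not know which round is active and which is sham". The Risks to Participants section says that participants are the only people blinded to sequence. Brain Stimulation and the Visit 2–11 description both say that "participants will be told that stimulations can feel and sound different", and both give as the reason a set of conditions that still includes M1.

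**Use of the contrast** (Data Analysis Plan): if the ANOVAs on app-rated pain are significant and the post-hoc comparison favours hippocampal stimulation, the approach is declared clinically important.

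**The concern.** The blind is argued from what the pulses feel like. Attaching an electrode to the scalp is a separate cue, and so is turning the coil over. In a parallel-group trial each participant would meet one set-up and have nothing to compare it with. Here each participant meets both, about three weeks apart, and rates their own pain throughout. If beliefs about the rounds differ systematically, expectation becomes part of the active-minus-sham difference, and no planned data would show that this had happened. The success rule would then rest on a contrast whose main protection was assumed and not built in.

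**Working it through.** The plan gives no figure on blinding to reproduce, so the check is mainly a comparison of the text.

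**1. What differs between the set-ups.**

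| Element | Active (Modality 1) | Sham (Modality 2) |
|---|---|---|
| Stimulation parameters | stated | same as active |
| Coil side | active side | flipped to sham side |
| Skin electrode near target | not mentioned | attached and delivering current |

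The Visit 2–11 description, Table 1 and the TMS safety section do not place an inactive electrode in active sessions. The TMS safety section gives a different account of sham, in which stimulation intensity is turned down to a low value. That conflicts with the same-parameters statement in Modality 2, and a change in intensity could itself be a cue.

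**2. Exposure.** 2 rounds × 5 sessions = 10 sessions: 5 planned with an electrode and 5 without. One missed session per round is tolerated, so a retained participant has at least 4 of each. This applies to all 12 planned completers (16 recruited).

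**3. Why random order does not help.** Let τ be the true active-minus-sham effect, π the period effect, and e_A and e_S the expectation shifts in the active and sham rounds.
- Sequence 1: mean difference = τ + π + (e_A − e_S)
- Sequence 2: mean difference = τ − π + (e_A − e_S)
- Average of the two: τ + (e_A − e_S)

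The period effect cancels. The expectation difference does not.

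**4. Size and direction.** If a share p_c identify the rounds correctly, a share p_w identify them wrongly, and belief shifts the pain difference by d, the bias is (p_c − p_w) × d. It is zero when p_c = p_w and reverses when p_w > p_c. The documents give none of the three quantities.

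**5. Sensitivity only.** With two conditions, the repeated-measures ANOVA is a paired t-test. Assume two-sided alpha 0.05 (the plan states none), no true effect, and a net shift of b standard deviations of the within-person difference, in either direction. The chance of a significant difference for one outcome is P(|T| > t(0.975, n − 1)), where T is noncentral t with noncentrality b√n.

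| b (assumed) | n = 12 | n = 16 |
|---|---|---|
| 0 | 5% | 5% |
| 0.2 | 10% | 12% |
| 0.35 | 20% | 26% |
| 0.5 | 35% | 47% |
| 0.8 | 71% | 85% |

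A shift towards active would create false superiority. A shift towards sham would hide a real effect.

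**6. What a treatment-guess question could show.** Test one guess per participant, one-sided, against 50%. With n = 12, at least 10 correct are needed: (66 + 12 + 1)/4096 = 0.019. The chance of reaching that is 25%, 56% or 89% if the true correct-guess rate is 70%, 80% or 90%. With n = 16, at least 12 correct are needed (p = 0.038), and the chances are 45%, 80% and 98%.

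**The case against.** The strongest reply is that perceiving a difference is not identifying sham. Participants are not said to be told which set-up is real, and some could take a current-delivering electrode as the sign of active treatment. This stands. A reader might infer that the blind is broken, or that the bias must favour active stimulation by some number of pain points. The documents support neither, because the net effect depends on correct minus wrong identifications and on an expectation effect that nobody has measured.

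Other points have force:
- Calling the set-ups visibly different goes too far, since an electrode near a parietal site may be out of the wearer's sight. Its attachment would still be noticed, so perceptibly different is the supportable term.
- The absence of an electrode in active sessions is inferred from the exception clause and from silence. If one is in practice worn in both rounds, only the text is at fault.
- It is tempting to argue that motor-threshold testing teaches participants what real TMS is like. Single pulses over motor cortex are a poor reference for 20 Hz trains over parietal cortex, so I place no weight on this.
- The warning that sessions may feel and sound different may work as cover, since it names no condition as real. Its reference to M1 is out of date, but that does not show that it unblinds anyone.
- Study Endpoints makes connectivity the main aim and pain secondary, and connectivity is less directly exposed to expectation. The Power Calculation section describes the data as preliminary.

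The reply does not remove the core problem. The only stated support for the blind covers sensation, and the plan attaches a strong declaration to self-rated pain.

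**Conclusion.** The concern holds in this form: as written, the two conditions differ perceptibly in set-up for every participant, so the claim that participants will not know which round is which is neither assured nor verified. It rests on reading the exception clause as it stands and on taking the active description as complete. No figure for the bias can be drawn from the documents. The sensitivity table shows only that, with 12 completers, an assumed net shift of 0.2 to 0.8 SD in either direction would raise the chance of a significant difference from 5% to between 10% and 71%.

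This should be fixed before enrolment. I do not rate it as a must-fix, because the main aim is connectivity. The pain-based declaration is what keeps it from being minor.

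**What to change.** 1. In both modality descriptions under Brain Stimulation, state that the same electrode, lead and skin preparation are used at the same place in every session of both rounds, with the electrode output off in active sessions, and that the coil side is set out of the participant's view.
2. In Brain Stimulation and the Visit 2–11 description, replace the wording that still lists M1 with one neutral sentence, used identically in both rounds.
3. Reconcile the same-parameters statement for sham with the reduced-intensity statement in the TMS safety section.
4. Optionally, add one treatment-guess item, asked once after the last app rating so that it does not prompt participants to look for cues between rounds. Questionnaires already go out by email link, so no extra visit is needed. Report it descriptively: with 12 participants it has limited ability to detect unblinding, and a guess may partly reflect perceived benefit. It does not replace matching the set-up, which cannot be done after data collection.

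Cost: one extra electrode and a few minutes of preparation per active session, some text changes and, if adopted, one questionnaire item.

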#### **Stimulation modality sequences:**

The order of the stimulation modalities will be different across subjects. Subjects will be randomly assigned to one of two possible groups/stimulation sequences (fig 1). Before enrollment starts, we will produce 18 envelopes containing the stimulation sequence (see below possible combinations; we expect to use only 16). The stimulation sequence will be kept in sealed envelopes; therefore, subjects will get their assignment according to the order of entrance in the study. The study coordinator will retain the original sequence list which will be kept in a locked place. The study staff who provides the stimulation TMS session will be the only un-ed personnel.

STU#:

[figure not shown]

Figure 1: Study design and stimulation sequence. The subjects will be allocated to 1 envelop according to the entrance in the study. All participants will receive all the 2modalities of stimulation. Each round is composed by 5 daily session of stimulation, participants will not know which round is active and which is sham. Participants randomized to group 1 will have a second MRI at visit 6; and participants randomized to group 2 at visit 11.

## PROCEDURES INVOLVED:

### General Overview

Participants will be enrolled after meeting all inclusion/exclusion criteria including an NRS (0-10 pain score) >4/10 for back pain and no contra-indications to the rTMS stimulation and MRI exam.

### Detailed Study Outline

- **Pre-screening Procedures:**

During the pre-screening process, the subject will contact a study staff (or vice-versa) usually via phone call or email. During this call, the co-investigator will discuss in greater depth the details of the study, explain the study procedures and encourage the subject to ask questions. In the privacy of the laboratory, the co-investigator will ask the subject questions from the following:

- Phone screening questionnaire
- **Visit 1** - (Approx. Time: 2-3 hours)

